### 5.3 Recruitment policy

A total of 30 participants will be recruited to complete this study, although the recruitment aim will be at least 35 to account for drop out. Recruitment will run for 11 months from October 2018 through August 2019, following successful ethical approval and funding applications. This will allow for preparation and sequencing of final samples and analysis of data before September 2020, with the final study appointments finishing in April 2020.

#### 5.3.1 Recruitment from the NOAR

Potential participants will be identified primarily via the incoming stream of GP referrals to the Early Arthritis Clinic at NNUH received by the Norfolk Arthritis Register (NOAR); an ongoing inception cohort of inflammatory arthritis patients in Norfolk, by [name] (NOAR Clinical Manager and Research Nurse). NOAR was established in 1989 and investigates the development and treatment of inflammatory polyarthritis along its natural course. More than 4,000 patients are registered in NOAR, which involves longitudinal 12-monthly study visits where the Research Nurse collects information on historical and current health and joint symptoms and takes a blood sample. Further information on NOAR can be found in the NOAR protocol (Appendix 13) and at the NNUH website: <http://www.nnuh.nhs.uk/departments/rheumatology/norfolk-arthritis-register/>

##### 5.3.1.1 NOAR participants meeting ACR 2010 criteria for RA

NOAR recruits approximately 18 participants per month, of which approximately 5 would potentially be suitable for this study as they meet ACR criteria for RA at baseline. Participants will be invited via the ongoing stream of referrals to NOAR, allowing around 55 participants to be invited to this study over the 11 month recruitment period. Existing NOAR members will also be invited to this study. As the NNUH appointments are part of an 18 week pathway, it will be possible to invite existing NOAR participants meeting the study criteria and recruited to NOAR within the last 4-5 months (approximately 25 potential participants), as they will not have had their initial appointment yet. This provides a minimum of 80 participants who can be invited to this study, which should be sufficient; alongside recruitment from GPs and Rheumatology Clinicians, to obtain 35 participants.

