##### 5.3.1.2 Recruitment procedure from NOAR

Figures 2 and 3 shows representations of the study timeline from the Study Team and participants point of view, respectively. A patient presenting to their GP with inflammatory arthritis and being referred to the Early Arthritis Clinic at NNUH will be notified to NOAR as part of their normal recruitment procedure, and at the same time as sending out the NOAR participant information sheet and consent form (Appendix 14 and 15); if they meet the eligibility criteria for this study, the NOAR Research Nurse will also send out an invitation letter (Appendix 2), Participant Information Sheet (PIS) (Appendix 3) containing a response slip, watermarked versions of the consent forms (Appendix 24 and 25) and prepaid envelope for the MyRA study. If a positive response slip is received, the participant will be contacted via telephone by [name] or [name] to discuss the study further and explain what will happen at their first Early Arthritis Clinic appointment. Existing NOAR members suitable for this study; who have not yet had their initial NNUH Early Arthritis Clinic appointment, will also be identified by the NOAR Research Nurse and a copy of the MyRA invitation letter (Appendix 2) and PIS (Appendix 3) will be sent to them inviting them to the study, along with watermarked versions of the consent forms (Appendix 24 and 25) so they may review these prior to their first study visit if they chose to take part.

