## 5.4 Eligibility criteria

### 5.4.1 Inclusion criteria

- 18-65 years of age
- RA diagnosis based on ACR 2010 classification criteria with symptoms starting within the last 2 years
- Referred by GP to the Early Arthritis Clinic at NNUH
- Commencing methotrexate monotherapy for the first time

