### 5.4.2 Exclusion criteria

- *Initially* commencing combination therapy (prior to first stool sample) rather than methotrexate monotherapy i.e. MTX combined with another DMARD or prednisolone
- Commencement of MTX therapy prior to first stool sample or cessation of MTX therapy at any point during the study
- History of psoriasis
- Those currently suffering from, or have ever suffered from, any diagnosed gastrointestinal disease, gastrointestinal disorders including regular diarrhoea and constipation (excluding hiatus hernia unless symptomatic) and/or have undergone gastrointestinal surgery.
- Those regularly (3+ times/week) taking self-prescribed over the counter medications for digestive/gastrointestinal conditions
- Use of laxatives within 7 days prior to sampling unless these have been used on a regular basis (3+ times/week) for more than one month prior to the study and will continue to be used throughout the study period
- The use of over-the-counter medications or food/drinks containing pre and/or probiotics within 7 days prior to sampling, unless these have been used on a regular basis (3+ times/week) for more than one month prior to the study and will continue to be used throughout the study period
- Significant alteration of the participant's normal diet at any point during the study (e.g. adoption of the 5:2 fasting diet)
- Regular (3+ times/week) or recent (within 3 months) use of colonic irrigation or other bowel cleansing techniques
- Recently returned to the UK following a period abroad, and who have suffered gastric symptoms during the period abroad or on return to the UK. These will be assessed on an individual basis
- Currently taking or finished a course of antibiotics within the last 3 months
- Currently pregnant or lactating
- Living with or related to any member of the Study Team
- Those who have limited or no understanding of spoken and written English

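### Does the count of 80 NOAR invitees in Protocol 5.3.1.1 undermine the target of 35 recruits and the 82.5% power?

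*Protocol*

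**What the plan says.** Section 5.3.1.1 of the Protocol starts from about 18 NOAR recruits a month, "of which approximately 5 would potentially be suitable for this study as they meet ACR criteria for RA at baseline". Over 11 months that gives about 55. It then adds a waiting list. Because first appointments follow an 18-week pathway, "it will be possible to invite existing NOAR participants meeting the study criteria and recruited to NOAR within the last 4-5 months", put at about 25. The total is presented as "This provides a minimum of 80 participants who can be invited to this study, which should be sufficient". The same sentence goes on to name GPs and rheumatology clinicians as further sources for the 35, and section 5.3.2 describes that route as additional to NOAR.

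Section 5.3.1.2 restricts the mailing: "if they meet the eligibility criteria for this study, the NOAR Research Nurse will also send out an invitation letter". Section 5.4 sets conditions beyond ACR classification, among them "18-65 years of age" and an exclusion for starting on combination treatment "rather than methotrexate monotherapy i.e. MTX combined with another DMARD or prednisolone".

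Section 5.3 runs recruitment from October 2018 through August 2019, with last visits in April 2020. Section 5.5.1.1 takes consent at the first clinic visit, or at the Nurse Practitioner visit for patients identified at that clinic. Section 7.1 requires 30 completers from 35 recruits for 82.5% power at a correlation of 0.5.

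**The concern.** Three features make the 80 look too high.

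- **Eligibility.** The monthly rate of 5 reflects ACR criteria alone, whereas invitation and entry depend on all of section 5.4. The 25 existing members are described as meeting the study criteria, yet they equal the same ACR-only rate over 5 months.
- **Timing.** The sum counts patients already waiting when the study opens but does not take off those still waiting when it closes. Consent comes at the clinic, so an invitation late in the window does not give a recruit within it.
- **Overlap.** Every participant must satisfy "Referred by GP to the Early Arthritis Clinic at NNUH", and a patient "being referred to the Early Arthritis Clinic at NNUH will be notified to NOAR as part of their normal recruitment procedure". The GP and clinician routes may therefore reach many of the same people.

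Section 5.3.1.1 is the only place where the protocol argues that 35 can be reached. If the usable pool is nearer 55, and if 35/80 is taken as the expected yield, the study would finish with about 21 participants and about 65% power. On that reading the protocol would have to extend recruitment, show other recruits or state a lower power.

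**Working it through.** **1. The protocol's power figure.** Inputs from section 7.1: r = 0.5, n = 30, alpha 0.05 (taken as two-sided), the *pwr* package in R. That package's correlation routine uses

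- critical r: r_c = sqrt(t² / (t² + n − 2)), with t the 97.5% point on n − 2 degrees of freedom;
- z = atanh(r) + r / (2(n − 1));
- power = Φ((z − atanh r_c) × sqrt(n − 3)), plus a negligible opposite tail.

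At n = 30: t = 2.048, r_c = 0.361, atanh r_c = 0.378, z = 0.549 + 0.009 = 0.558. Then (0.558 − 0.378) × sqrt(27) = 0.935, and Φ(0.935) = 0.825. The stated 82.5% is reproduced. Drop-out also agrees: 30 / (1 − 5/35) = 35.

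**2. The pool as written.** 5 × 11 = 55 and 5 × 5 = 25, so 80. With a 4-month backlog it is 55 + 20 = 75. The 80 is therefore not a minimum even on its own inputs.

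**3. First clinics inside the window.** With a wait of w months, those seen in 11 months are the opening backlog, 5w, plus new referrals seen in time, 5(11 − w). The sum is 55 for any w up to 11.

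**4. If April 2020 is the binding limit.** Figure 4 places the last visit at weeks 24-27.

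- First clinic on 31 August 2019: last visit 15 February to 7 March 2020, so April leaves slack.
- Last visit on 30 April 2020: first clinic as late as 24 October (27 weeks) to 14 November 2019 (24 weeks), about 64 to 67 patients at 5 a month.
- Last visit on 1 April 2020 at 27 weeks: first clinic by 25 September 2019, about 59 patients.
- Invitation on 31 August 2019 plus an 18-week wait: last visit 20 June to 11 July 2020, outside the timeline.

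**5. Yield needed if NOAR alone supplied all 35.**

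| NOAR patients | Yield needed for 35 |
|---|---|
| 80 | 35/80 = 44% |
| 67 | 35/67 = 52% |
| 64 | 35/64 = 55% |
| 59 | 35/59 = 59% |
| 55 | 35/55 = 64% |

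**6. Where 65% power comes from.** It applies 43.75% to 55 patients: 55 × 0.4375 = 24.1 recruits, × 30/35 = 20.6 completers, power 65.3% (66.2% at n = 21). The same yield on 64 gives 24.0 completers and 72.6%; on 67, 25.1 completers and about 75%.

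If x recruits come from other routes and the NOAR share shrinks by 55/80, recruits are x + (35 − x) × 55/80. For x = 10 this is 27.2 recruits, 23.3 completers and 71% power. For x = 17.5 it is 29.5, 25.3 and 75%.

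Each figure takes the yield that would just suffice with 80 and treats it as the yield expected. The protocol states no such yield; at 64%, 55 patients supply 35.

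**7. People outside the count of 5 a month.** Section 5.3.1.2 mails the study invitation together with the NOAR consent papers, so it reaches eligible referrals who may never join NOAR. Of 18 NOAR recruits a month, about 18 − 5 = 13 do not meet ACR criteria at NOAR baseline. Section 5.4.1 does not tie the classification to that moment, and section 5.3.2 lets a clinician introduce the study at the first clinic, so some of the 13 may qualify later. These groups push the pool up while the other criteria push it down. The documents do not give the net effect.

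**The case for a change.** The strongest case for a change is that every visible choice in the sum leans the same way: the top of the backlog range, ACR criteria only, and no closing backlog. No uptake rate, eligible share or GP number offsets this. The eligible share could decide the matter: if fewer than 35/55 = 64% of ACR-positive patients met the rest of section 5.4, 55 of them could not supply 35 even at full uptake. As an illustration resting on an assumed range, a share of 60-90% turns 55 into 33-50 patients.

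The criticism of the word minimum stands, and so does the point that invitations exceed the patients who can consent in time. Three parts do not stand.

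- The 80 is not shown to be an upper bound, because the protocol admits entrants outside the ACR-at-baseline count.
- The 44% is only 35/80, the yield needed if the other routes gave nobody. It is not a rate the protocol states or implies, since its sentence relies on those routes too.
- The 82.5% is stated for 30 completers and is right for 30 completers. A shortfall in recruitment would lower the power achieved but would not make that statement wrong.

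**Conclusion.** The wording is optimistic, but no change to the plan follows. A fair reading is that about 75-80 NOAR patients can be invited and about 55-67 can reach first clinic within the study timeline. The yield needed from NOAR alone is then about 52-64%, less whatever the GP and clinician routes contribute. This assumes a flat 5 a month and the visit weeks in Figure 4; Figures 2 and 3 could not be seen.

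The possible remedies gain little.

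- Rewording the sentence changes no result.
- Adding eligibility, uptake and GP numbers fills in feasibility detail that the study team can track as recruitment proceeds.
- Extending consent until 80 patients have had a first clinic takes 80/5 = 16 months, to 31 January 2020, with last visits 17 July to 7 August 2020. That leaves 25 to 46 days before 1 September 2020, against about 18 weeks from the end of April. It is a trade-off for the sponsor, not a correction.
- Restating power at about 21 completers would replace a correct conditional figure with a scenario built on an assumed yield.

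The estimand, the primary test and the stated sample size are unaffected.

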##### 5.3.1.2 Recruitment procedure from NOAR

Figures 2 and 3 shows representations of the study timeline from the Study Team and participants point of view, respectively. A patient presenting to their GP with inflammatory arthritis and being referred to the Early Arthritis Clinic at NNUH will be notified to NOAR as part of their normal recruitment procedure, and at the same time as sending out the NOAR participant information sheet and consent form (Appendix 14 and 15); if they meet the eligibility criteria for this study, the NOAR Research Nurse will also send out an invitation letter (Appendix 2), Participant Information Sheet (PIS) (Appendix 3) containing a response slip, watermarked versions of the consent forms (Appendix 24 and 25) and prepaid envelope for the MyRA study. If a positive response slip is received, the participant will be contacted via telephone by [name] or [name] to discuss the study further and explain what will happen at their first Early Arthritis Clinic appointment. Existing NOAR members suitable for this study; who have not yet had their initial NNUH Early Arthritis Clinic appointment, will also be identified by the NOAR Research Nurse and a copy of the MyRA invitation letter (Appendix 2) and PIS (Appendix 3) will be sent to them inviting them to the study, along with watermarked versions of the consent forms (Appendix 24 and 25) so they may review these prior to their first study visit if they chose to take part.

#### 5.3.2 Recruitment from the participant's GP or NNUH Rheumatology Clinician

In addition to NOAR, MyRA participants will be recruited directly via the patient's own GP or NNUH Rheumatology Clinician. GPs and clinicians will be provided with study information to give to

potential participants entering their clinics who might fit the eligibility criteria. Participating GPs and clinicians will be provided with this Study Protocol so they may answer brief questions about the study, but potential participants will still be asked to return the response slip to QIB and will receive a telephone call from [name] or [name] prior to visiting NNUH for their initial Early Arthritis Clinic appointment. If a potential participant is recruited from their initial Early Arthritis Clinic appointment at NNUH and responds positively using the response slip, they will receive the telephone call prior to their Nurse Practitioner appointment at NNUH.

## 5.4 Eligibility criteria

### 5.4.1 Inclusion criteria

- 18-65 years of age
- RA diagnosis based on ACR 2010 classification criteria with symptoms starting within the last 2 years
- Referred by GP to the Early Arthritis Clinic at NNUH
- Commencing methotrexate monotherapy for the first time

### 5.4.2 Exclusion criteria

- *Initially* commencing combination therapy (prior to first stool sample) rather than methotrexate monotherapy i.e. MTX combined with another DMARD or prednisolone
- Commencement of MTX therapy prior to first stool sample or cessation of MTX therapy at any point during the study
- History of psoriasis
- Those currently suffering from, or have ever suffered from, any diagnosed gastrointestinal disease, gastrointestinal disorders including regular diarrhoea and constipation (excluding hiatus hernia unless symptomatic) and/or have undergone gastrointestinal surgery.
- Those regularly (3+ times/week) taking self-prescribed over the counter medications for digestive/gastrointestinal conditions
- Use of laxatives within 7 days prior to sampling unless these have been used on a regular basis (3+ times/week) for more than one month prior to the study and will continue to be used throughout the study period
- The use of over-the-counter medications or food/drinks containing pre and/or probiotics within 7 days prior to sampling, unless these have been used on a regular basis (3+ times/week) for more than one month prior to the study and will continue to be used throughout the study period
- Significant alteration of the participant's normal diet at any point during the study (e.g. adoption of the 5:2 fasting diet)
- Regular (3+ times/week) or recent (within 3 months) use of colonic irrigation or other bowel cleansing techniques
- Recently returned to the UK following a period abroad, and who have suffered gastric symptoms during the period abroad or on return to the UK. These will be assessed on an individual basis
- Currently taking or finished a course of antibiotics within the last 3 months
- Currently pregnant or lactating
- Living with or related to any member of the Study Team
- Those who have limited or no understanding of spoken and written English

## 5.5 Study procedures

### 5.5.1 First appointment: Early Arthritis Clinic

#### *5.5.1.1 Informed consent*

At the participant's first Early Arthritis Clinic appointment, any member of the Study Team appropriately trained in taking Informed Consent will be present to ensure the participant knows what the study involves and has read and understood the PIS before asking for written Informed Consent, both for participation in the study and for long-term storage of samples at the Norwich Research Park (NRP) Biorepository (Appendix 4 and 5). The consent to store samples long-term in the NRP Biorepository is completely optional. Alternatively, the Rheumatology Clinician in charge of the participant's care may take written Informed Consent on behalf of the study team. The clinicians will have copies of this protocol and will have completed mandatory General Clinical Practice (GCP) training which involves guidelines for taking Informed Consent. Consent will not be sought from potential participants who heard about the study for the first time on the same day.

If the participant is identified by their Rheumatology Clinician at their initial Early Arthritis Clinic appointment and responds positively to the invitation letter, they will not provide informed consent at this stage. Therefore, informed consent for these participants will be taken at their Nurse Practitioner (NP) appointment by an appropriately trained member of the study team before taking the first study samples. Watermarked versions of the consent forms (Appendix 24 and 25) will be posted to the participant prior to this appointment for them to review and they will have had an initial telephone call with a member of the study team.

After consent, a letter to the participant's GP will be generated to inform them of their patient's involvement with MyRA (Appendix 6). The participant will have agreed to this and provided their GP details as part of the consent process.

#### *5.5.1.2 Providing initial study materials*

The participant will then be provided with a stool collection kit containing a home stool collection device (Fecotainer), a clear plastic zip-lock bag to place the Fecotainer in and instructions for taking the stool sample (Appendix 7). A 7-day food diary (Appendix 8) will be provided to be completed the week prior to the participant's Nurse Practitioner (NP) appointment (approximately 3 weeks after their first Early Arthritis Clinic appointment), where they will commence methotrexate (MTX) treatment as part of their normal clinical care. Participants will be asked to bring a fresh stool sample to the NP appointment (collected within 2 hours of the appointment), or if they are unable to do this they may wish to organize collection of the stool sample with [name] or [name] either the day before their NP appointment, or the day after provided they have not yet begun MTX treatment at the time.

#### *5.5.1.3 Collection of samples and data if the participant is started on methotrexate at their first Early Arthritis Clinic appointment*

Should the Rheumatology Clinician begin their patient on MTX at this first appointment; without arranging an NP appointment, stool and blood samples may be collected at this time point (if the clinician agrees it is suitable to do this prior to commencing the first dose of MTX). Collection of samples and data would be as per Section 5.5.2.1, 5.5.2.2 and 5.5.2.3, except the participant would be asked to fill in the 7-day food diary from this point forward and bring it to their next Routine Treatment Review where the study team will be present. In this case, the participant would then only be seen at their 3 and 6-month Routine Treatment Review appointments (Section 5.5.3) and not at an NP appointment. No samples or data will be collected before the participant has provided written informed consent to take part in this study.

### 5.5.2 Second appointment: Nurse Practitioner

As part of their normal care pathway, the participant will commence MTX treatment after this appointment. Should the participant or their clinician decide for any reason not to commence MTX treatment, they would be excluded from the study from this point. If continuing the study, participants will be provided with another stool collection kit at the end of this appointment (Fecotainer, instructions for use [Appendix 7], clear plastic zip-lock bag). No further 7-day food diaries will be provided.

#### 5.5.2.1 Collection of stool sample

At the participant's NP appointment their stool sample will be taken from them by a member of the study team, if they were able to produce this sample within the 2 hours prior to this appointment. If this was not possible, collection of a fresh stool sample from the participant's location may be organized between the participant and [name] or [name] for the following day, provided the sample is produced prior to the participant taking their first dose of methotrexate. If the participant was consented at their NP appointment, they will be asked to produce a stool sample before taking their first dose of methotrexate. The participant will be asked to bring another fresh stool sample (taken within 2 hours) to their next appointment in 3 months' time, or to arrange collection of this sample at a time more suitable to them, using the stool collection kit provided.

